1.5 Rationale for treatment regimen

The AIS dosing regimen is twice a day IV infusion of 30 mg administered over 30 minutes for up to 14 days. In a similar dosing regimen (0.5 mg/kg of MCI-186 IV infusion over 30 min), C_{max} and AUC of unchanged MCI-186 in healthy elderly subjects were 1041 ng/mL and 725 ng·h/mL, respectively (Table 2). The ALS dosing regimen is once a day IV infusion of 60 mg administered over 60 minutes for 14 days or 10 treatment days over 2 weeks followed by a 2-week drug-free period. Simulated C_{max} and AUC for the ALS regimen were 1049 ng/mL and 1374 ng·h/mL, respectively^[2].

The dose in this study is a single dose of 30 mg MCI-186 intravenously administered over 60 minutes. Simulated C_{max} and AUC for the 30 mg dose level in healthy subjects are 470 ng/mL and 600 ng·h/mL, respectively^[2]. The Sponsor set the 30 mg dose level to ensure the subjects' safety as the effect of severe hepatic impairment on PK profile is unclear.

In addition, dose proportionality for MCI-186 was assessed by simulation data from a PPK model. The plasma concentrations of MCI-186 following the administration of 10, 30, 60 and 120 mg/hour/body dosing were simulated for 1000 subjects in each dosing group. The PK parameters C_{max} and area under the concentration-time curve from time zero to infinity ($AUC_{0-\infty}$) were calculated from the simulated plasma concentration of MCI-186 using a non-compartmental analysis and the analysis of dose proportionality (linearity) was carried out using a power model. The results of the power model are shown in Table 4. From a statistical viewpoint, C_{max} and $AUC_{0-\infty}$ did not exhibit dose-proportionality in the range of 10 to 120 mg as the 95% confidence interval (CI) for the slopes did not include the value 1. Conversely, the regression expressions for Dose- C_{max} and Dose- $AUC_{0-\infty}$ were $\text{Log}(C_{max}) = 1.1375 * \text{log}(\text{Dose}) + 2.2800$ and $\text{Log}(AUC_{0-\infty}) = 1.1595 * \text{log}(\text{Dose}) + 2.5216$, respectively. These results imply that when the dose is doubled, C_{max} and $AUC_{0-\infty}$ are increased by 2.20 and 2.32 times, respectively.

Table 4 Analysis of dose-proportionality

Parameter	Slope	95% confidence interval
C_{max}	1.1375	1.1337 - 1.1412
$AUC_{0-\infty}$	1.1595	1.1547 - 1.1643

For the reasons stated above, the PK of MCI-186 is almost linear and the PK of 60 mg MCI-186 infused over 60 minutes can be extrapolated from the results of 30 mg MCI-186 infused over 60 minutes. Therefore, it is possible to evaluate PK in all subjects who will be administered 30 mg of MCI-186.

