1.3 Clinical studies

MCI-186 was evaluated in five Phase I studies in healthy subjects in Japan and Europe, eight clinical studies in AIS subjects in Japan, Europe and Korea, three clinical studies in

subarachnoid haemorrhage subjects in Japan and five clinical studies in ALS subjects in Japan.

A single-dose, Phase I study (0.2 to 2.0 mg/kg) in which IV infusion was performed for 40 minutes or 3 hours in Japanese healthy adult males and a repeated-dose study (1.0 mg/kg/day, 7 days) were conducted to investigate safety and PK. Although abnormal changes in laboratory data were reported in two subjects in the single-dose study, the values were found to have returned to normal in follow-up examinations. The C_{max} and AUC were proportional to dose, half-life ($t_{1/2}$) and urinary excretion rate were substantially constant regardless of dose, and there was no difference in PK between single dose and repeated doses (Table 1). Thus, no accumulation of MCI-186 in plasma concentration was observed following repeated doses.

Table 1 Pharmacokinetic parameters of unchanged MCI-186 in Japanese healthy male subjects after single or repeated intravenous infusion (once daily for 7 days)*

Parameter	Dose						
	Single dose					Repeated dose (1.0 mg/kg/40 min)	
	0.2 mg/kg/ 40 min	0.5 mg/kg/ 40 min	1.0 mg/kg/ 40 min	1.5 mg/kg/ 40 min	2.0 mg/kg/ 3 hours	First dose	Final dose
Plasma concentration of unchanged MCI-186 at the time of the completion of administration (ng/mL)	223	659	1727	3061	1226	1616	1736
$t_{1/2\alpha}$ (h)	0.17 (0.19)	0.15	0.17	0.17	0.12	0.14	0.14
$t_{1/2\beta}$ (h)	1.45 (1.49)	1.45	0.85	0.81	0.65	0.89	0.78
$t_{1/2\gamma}$ (h)	-	-	4.50	5.16	4.38	6.01	5.71
AUC (ng·h/mL)	201† (184)†	581†	1537‡	3005‡	3717‡	1474‡	1669‡

* Values are means; N = 5; - indicates not calculated; Data in brackets were calculated from values after the completion of administration; † AUC 0-8 h; ‡ AUC 0-24 h

In a repeated-dose study (0.5 mg/kg/30 min, twice daily, 2 days) in Japanese healthy male elderly and adult subjects, the PK parameters of unchanged MCI-186 and metabolites in plasma were comparable between elderly and adult males (Table 2), and there was no change in urinary excretion. In addition, there was no difference in safety profile between the elderly and adult male subjects, and no notable clinically significant findings.

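### Does the misprinted AUC dose-doubling factor (2.32, where the slope gives 2.23) undermine reading 60 mg exposure from a 30 mg study?

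*Protocol*

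**What the plan says.** Protocol section 1.5 reports a simulation from the population PK model with 1000 subjects at each of 10, 30, 60 and 120 mg per hour, analysed with a power model. Table 4 gives a Cmax slope of 1.1375 (95% CI "1.1337 - 1.1412") and an AUC0-∞ slope of 1.1595 (95% CI "1.1547 - 1.1643"). Because neither interval contains 1, the text states that the two parameters "did not exhibit dose-proportionality in the range of 10 to 120 mg". It then gives the size of the departure: on doubling the dose, Cmax and AUC "are increased by 2.20 and 2.32 times, respectively". The section concludes that "the PK of MCI-186 is almost linear and the PK of 60 mg MCI-186 infused over 60 minutes can be extrapolated" from the 30 mg results.

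The same section gives simulated exposures of 470 ng/mL and 600 ng·h/mL for 30 mg over 60 minutes, and 1049 ng/mL and 1374 ng·h/mL for the 60 mg ALS regimen.

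Section 1.3, describing an earlier Phase I study in healthy Japanese men, says that Cmax "and AUC were proportional to dose" and refers to Table 1.

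**The concern.** Three things look wrong together. The AUC doubling factor does not follow from the slope printed next to it. A section that reports the failure of dose-proportionality ends by calling the kinetics nearly linear. And section 1.3 asserts proportionality although exposure per mg/kg in Table 1 rises with dose.

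The study gives 30 mg while the ALS regimen is 60 mg, so a reader may ask whether the findings carry over. If someone simply doubled the 30 mg exposures, 60 mg exposure would be understated. If the slope itself rises with exposure, the ratio of impaired to normal seen at 30 mg might not hold at 60 mg.

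**Working it through.** **Inputs.** Slopes and confidence limits: Protocol 1.5, Table 4. Simulated exposures: Protocol 1.5. Observed means (N = 5 per dose): Protocol 1.3, Tables 1 and 2.

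**1. The doubling factors.** In a power model, exposure = a × dose^b, so doubling the dose multiplies exposure by 2^b. The intercept and the log base cancel.

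- Cmax: 2^1.1375 = 2.20. The protocol's figure is reproduced.
- AUC0-∞: 2^1.1595 = 2.234. Over the slope's interval, 2^1.1547 = 2.226 to 2^1.1643 = 2.241. The printed 2.32 is not reproduced.
- A factor of 2.32 needs a slope of log2(2.32) = 1.214, above the upper limit of 1.1643.
- Size of the slip: 2.32 / 2.234 = 1.039, about 4% too high.

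The cause may be 2 × 1.1595 = 2.319 or transposed digits. The documents do not say.

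**2. Direction.** The excess over exact proportionality per doubling is 2.200/2 − 1 = 10.0% for Cmax and 2.234/2 − 1 = 11.7% for AUC. The printed factor would imply 2.32/2 − 1 = 16%. Correction therefore moves AUC towards linearity.

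**3. Agreement with the simulated exposures.** 1049/470 = 2.23 for Cmax and 1374/600 = 2.29 for AUC. Both are modestly above 2, in line with the slopes.

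**4. What plain doubling would cost.** The understatement of 60 mg exposure is 1 − 2/2.200 = 9.1% (Cmax slope), 1 − 2/2.234 = 10.5% (AUC slope) or 1 − 2/2.29 = 12.7% (simulated AUCs). Neither document says that 30 mg exposures will be multiplied by 2.

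**5. Table 1, single doses over 40 minutes.** Local slope = ln(exposure ratio) / ln(dose ratio).

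| Step (mg/kg) | Dose ratio | End-of-infusion concentration | Slope | AUC | Slope |
|---|---|---|---|---|---|
| 0.2 to 0.5 | 2.5 | 223 to 659 (2.96) | 1.18 | 201 to 581 (2.89) | 1.16 |
| 0.5 to 1.0 | 2.0 | 659 to 1727 (2.62) | 1.39 | 581 to 1537 (2.65) | 1.40 |
| 1.0 to 1.5 | 1.5 | 1727 to 3061 (1.77) | 1.41 | 1537 to 3005 (1.96) | 1.65 |

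The middle AUC step compares AUC over 0–8 h with AUC over 0–24 h, so its slope is inflated by an unknown amount. The last step uses the same window and infusion time for both doses and still shows a 1.96-fold rise for a 1.5-fold dose. Section 1.3's description is therefore loose.

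**6. A cross-check against Table 2.** AUC0-∞ at 0.5 mg/kg in healthy adult men is 742, or 742/0.5 = 1484 per mg/kg. Table 1 at 1.0 mg/kg gives 1537 per mg/kg. The ratio is 1537/1484 = 1.04, close to proportional. For an assumed 60 kg subject this is the 30 to 60 mg step (0.5 × 60 = 30; 1.0 × 60 = 60). The comparison crosses studies, infusion times (30 against 40 minutes) and AUC definitions, so it is only indicative.

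**7. The ratio between groups.** If group g has exposure a_g × dose^b with a common b, the ratio of impaired to normal is a_1/a_2 at every dose, whatever b is. With different exponents, the ratio at 60 mg equals the ratio at 30 mg multiplied by 2^(b_1 − b_2). The documents give no information on whether b differs by group.

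**8. Where the factor is used.** The sample size (Protocol 10.1, SAP 3.3) is not based on a power calculation. The group comparison (Protocol 10.3.5.1; SAP 8.4.2) is a ratio of geometric means with a 90% confidence interval, both groups receiving 30 mg. The primary objective (Protocol 2.1.1, SAP 2.1.1) is stated at that dose. None of these takes 2.20 or 2.32 as an input.

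**The case for a change.** The best case for acting is that the error is certain, the correction costs one number, and section 1.5 is the protocol's own bridge to the 60 mg regimen. That bridge sets no criterion for near-linearity and does not say whether extrapolation means doubling, the power factor or the population model. Table 1 suggests a slope that climbs with dose, which a single exponent cannot represent. The simulation is not said to include subjects with hepatic impairment. Over the whole simulated range the slopes also accumulate: 12^1.1375 / 12 = 1.41 and 12^1.1595 / 12 = 1.49 from 10 to 120 mg.

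Some of this stands. The factor should be 2.23, section 1.3 describes Table 1 too generously, and the extrapolation method is unnamed.

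The rest is weaker. The failure of proportionality is reported openly, and with 1000 simulated subjects per dose the interval is so narrow that excluding 1 says little about size. The relevant step is one doubling, not a 12-fold range. The concentration step from 0.5 to 1.0 mg/kg would put the cost of plain doubling at 1 − 2/2.62 = 24%. That figure comes from means of five subjects given 40-minute infusions, and it applies to a method the protocol does not state. At the single dose of 1.0 mg/kg, Table 1 itself shows AUCs of 1537, 1474 and 1669. A changing ratio between groups is possible in principle, but nothing in the documents supports it.

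**Conclusion.** The arithmetic slip is real: 2.32 should read 2.23, a difference of about 4%. It is clerical. The correct slope and interval are in the same section, so any reader can recover the factor, and the error runs against the sponsor's conclusion. What remains is a 10 to 12% excess over proportionality per doubling, disclosed and reasonably described as a modest departure.

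No change to the plan follows. The factor sits in rationale text, no analysis or decision uses it, and the comparison at 30 mg would be the same with either number. The unnamed extrapolation method is a detail that analysts can supply from the printed slopes or the population model; a 60 mg prediction for impaired subjects is not among the study's objectives.

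This rests on two assumptions: the slopes in Table 4 are the correct figures and the factor is the misprint, and the study's conclusions are drawn at 30 mg. Constancy of the group ratio at 60 mg further assumes a common exponent, which this single-dose study cannot test.

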2 STUDY OBJECTIVES AND ENDPOINTS

2.1 Study objectives

2.1.1 Primary objective

The primary objective of this study is to assess the PK of MCI-186 after a single IV infusion of 30 mg/hour in subjects with severe hepatic impairment compared to subjects with normal hepatic function.

2.1.2 Secondary objectives

The secondary objective of this study is to investigate the safety and tolerability of MCI-186 in subjects with severe hepatic impairment and in subjects with normal hepatic function.

2.2 Study endpoints

2.2.1 Primary endpoints

The following primary PK parameters of MCI-186 will be calculated in the study:

- C_{max}
- Area under the concentration-time curve from time zero to the last quantifiable concentration (AUC_{0-last})
- $AUC_{0-\infty}$

2.2.2 Secondary endpoints

The following secondary endpoints will be evaluated during the study:

Pharmacokinetic parameters of MCI-186

- $t_{1/2}$
- Time to reach peak concentration (t_{max})
- Terminal elimination rate constant (λ_z)
- Total clearance (CL)
- Volume of distribution at steady state (V_{ss})
- Volume of distribution during the terminal phase (V_z)
- Mean residence time (MRT)
- Unbound area under the concentration-time curve from time zero to infinity ($AUC_{U0-\infty}$)
- Unbound total clearance (CLu)

Pharmacokinetic parameters of the the sulfate conjugate

- C_{max}
- AUC_{0-last}
- $AUC_{0-\infty}$
- $t_{1/2}$
- t_{max}

Safety and tolerability

- Incidence of adverse events (AEs) and serious adverse events (SAEs)
- Physical examination
- Vital signs (blood pressure, pulse rate and body temperature)
- 12-lead electrocardiogram (ECG) parameters

- Laboratory assessments including biochemistry, haematology, coagulation and urinalysis
- Columbia-Suicide Severity Rating Scale (C-SSRS; see Appendix 1 in Section 14)

3 STUDY DESIGN

3.1 Overall study design

This is a Phase I, open-label, single-dose study to evaluate the PK of MCI-186 in male and female subjects with severe hepatic impairment (Group 1, n = 6), defined using the Child-Pugh classification, and in male and female subjects with normal hepatic function (Group 2, n = 6). Subjects may be replaced or additional subjects may be enrolled to ensure a minimum threshold of 6 completing subjects per group.

- Group 1: Subjects with severe hepatic impairment (Child-Pugh total score of 10 to 14 [Grade C])
- Group 2: Healthy subjects with normal hepatic function to match Group 1 for age, body weight and gender

All subjects will be administered 30 mg MCI-186 over 60 minutes on the morning of Day 1. An infusion time window of ± 3 minutes is permitted.

Order of subject enrolment

Individual matching of healthy subjects will be performed for the subjects with hepatic impairment. Therefore, after the end of study assessments are completed in subjects with hepatic impairment, healthy subjects will be enrolled. Each healthy subject will be individually matched with a hepatic impairment subject with respect to age (± 15 years), body weight ($\pm 20\%$) and gender. Matched healthy subjects may be recruited by any study site, not necessarily by the same site which recruited the subject with hepatic impairment.

If there are significant safety concerns, the study may be stopped as described in Section 4.5.

Study periods and duration of study

The study consists of:

- A pre-admission Screening period (Day -21 to Day -2)
- A treatment hospitalisation period (Day -1 to Day 3) with single IV infusion of 30 mg MCI-186 over 60 minutes (including an infusion time window of ± 3 minutes) on Day 1, and PK blood sampling until 48 hours post-dose. All subjects will be confined to the study centre from Day -1 to Day 3. Safety assessments will be performed until discharge.
- A Follow-up Period (Day 7 +2 days). An end of study assessment will be performed.

The duration of participation for each individual subject is expected to be up to 30 days.

3.2 Rationale for study design and treatment regimens

This is a Phase I, open-label, single-dose study. Blinding will not be used because the primary endpoint, the assessment of specified PK parameters, is not subject to bias from the participants or observers.

Both males and females will be included into the study. A gender effect will not be investigated.

Hepatic function of the subjects will be scored and classified using the Child-Pugh classification in accord with FDA and EMA guidance^[3,4].

The study design, including the chosen endpoints, follows the FDA and EMA recommendations for evaluating the effect of impaired hepatic function on PK. It is considered an appropriate design for the clinical evaluation of the PK, safety and tolerability of MCI-186 in this sub-population of special interest.

3.2.1 Risk:benefit statement

MCI-186 has been evaluated in five Phase I studies in healthy subjects in Japan and Europe, eight clinical studies in AIS subjects in Japan, Europe and Korea, three clinical studies in subarachnoid haemorrhage subjects in Japan and five clinical studies in ALS in Japan.

At present, around 5000 ALS subjects have been treated with MCI-186 in Japan, South Korea and the US, and there is no safety concern regarding hepatic function. While hepatic and renal disorders were reported in post-marketing in AIS patients, these events were not observed as clinically significant findings in AIS and ALS studies. The package insert for treatment of AIS and ALS in Japan states that MCI-186 is contraindicated in patients with severe renal impairment and should be administered with care in patients with hepatic impairment. Conversely, there are no contraindications or warnings to patients with renal or hepatic impairment in the package insert for treatment of ALS in the US.

The following high risk subjects are excluded: subjects 1) who are of advanced age (>75 years) or 2) who present with severe infection. In addition, the dose in this study is a single dose of 30 mg MCI-186 intravenously administered over 60 minutes (including an infusion time window of ± 3 minutes). This dose is half the approved daily therapeutic dosage for treatment of AIS or ALS.

Furthermore, this Protocol includes frequent assessment of clinical and laboratory parameters including BUN, creatinine, AST, ALT, ALP, LDH, CK, RBC count and platelet count. The study will be conducted at a study centre which specialises in conducting studies in subjects with hepatic impairment.

This is a PK study in healthy subjects and subjects with severe hepatic impairment. There are no direct benefits to the subject through participation in this study. However, they and other patients may benefit in future because the results of this study may ultimately guide appropriate use of MCI-186 in the drug labelling.

4 SELECTION AND WITHDRAWAL OF SUBJECTS

The Sponsor does not operate a Protocol waiver system for eligibility criteria.

4.1 Number of subjects

At least 12 subjects will be enrolled to ensure 6 subjects in each group will complete the study.

4.2 Recruitment methods

Subjects with hepatic impairment will be recruited from those patients already attending clinics for the treatment of hepatic function or may be identified from a review of relevant databases. Matched healthy subjects will be recruited from a database of volunteers at any study centre. All recruitment material will be approved by the Independent Ethics Committee (IEC) prior to implementation.

4.3 Inclusion criteria

A subject will be eligible for enrolment in the study if ALL of the following criteria apply:

All subjects

1. Able to provide written informed consent to participate in this study after reading the participant information sheet and Informed Consent Form (ICF), and after having the opportunity to discuss the study with the Investigator or designee.
2. Male or female subjects age 18 to 75 years (inclusive) at signature of the ICF.
3. In the Investigator's opinion, subject is able to understand the nature of the study and any risks involved in participation, and willing to cooperate and comply with the Protocol restrictions and requirements.
4. A body weight of ≥ 50 kg and a body mass index ([BMI] Quetelet index) ranging from 18 to 37 kg/m^2 (inclusive) at Screening and Day -1.
5. Female subjects who are:
 - a) postmenopausal for at least 1 year, confirmed by follicle-stimulating hormone (FSH) assessment ($>40 \text{ mIU/mL}$), or
 - b) surgically sterilised (hysterectomy, bilateral oophorectomy or salpingectomy), or
 - c) congenital sterility.

Female subjects of child-bearing potential must use a highly effective method of contraception (see Section 4.7.5) from the Screening Visit or at least 2 weeks before Investigational Medicinal Product (IMP) administration, until 30 days after IMP dosing. Male subject must practice effective contraception from the time of IMP dosing until 90 days after IMP dosing. Adhering to strict abstinence is considered an accepted contraceptive method.

Hepatic impaired subjects (in addition)

6. Diagnosis of cirrhosis due to parenchymal liver disease, which is documented in the medical history and physical examination and confirmed by at least one of the following: hepatic ultrasound, computed axial tomography scan, magnetic resonance imaging and/or liver biopsy. A Child-Pugh classification score of 10 to 14 obtained during the Screening period (i.e., within 21 days of IMP administration).

7. Chronic (>6 months) and stable hepatic impairment defined as no clinically significant change in disease status at least 14 days before Screening.
8. Acceptable clinical conditions in the opinion of the Investigator on the basis of a physical examination, medical history, 12-lead ECG, vital signs and clinical laboratory tests (biochemistry, haematology, coagulation and urinalysis) at Screening, Day -1 and pre-dose on Day 1. Subjects with stable mild chronic concurrent diseases, such as degenerative joint disease, controlled diabetes, hypertension or hyperlipidaemia, etc. may be included.

Healthy subjects (in addition)

9. Subjects with normal hepatic function confirmed with tests within the normal reference range or results with minor deviations which are not considered by the Investigator to be clinically significant.
10. Good health and free from clinically significant illness or disease in the opinion of the Investigator on the basis of a physical examination, medical history, ECG, vital signs and clinical laboratory tests (biochemistry, haematology, coagulation and urinalysis) at Screening, Day -1 and pre-dose on Day 1.

4.4 Exclusion criteria

A subject will NOT be eligible for this study if ANY of the following criteria apply:

All subjects

1. Presence or history of severe allergy to food, or any medical product or relevant excipient that is of clinical significance.
2. Subjects who have previously been administered MCI-186.
3. As a result of the medical screening process, the Investigator considers the subject not suitable for the study.
4. Clinically significant 12-lead ECG abnormalities, including but not limited to, corrected QT interval using Fridericia's formula (QTcF) of >450 ms (male subjects) or >470 ms (female subjects) at Screening, Day -1 or before dosing.
5. Any other history or condition (surgical or medical) of disease which will increase the risk to the subject, will affect the PK of the study drug or will otherwise influence the assessments to be made in this study, in the opinion of the Investigator. Subjects who have undergone cholecystectomy may be included.
6. History of drug abuse or tested positive for alcohol or drugs of abuse at Screening and Day -1, excluding drugs which may cause a positive drugs or abuse test if medically indicated or prescribed.
7. Subjects who regularly, or on average, drink more than 35 units of alcohol per week (one unit is equivalent to 300 mL beer, 25 mL of spirits or 150 mL of wine).
8. Presence of active infection requiring antibiotics.
9. Positive test for human immunodeficiency virus (HIV) antigen/antibody at Screening.

10. Donation of one or more units of blood (450 mL) within 3 months prior to Screening, or plasma in the 7 days prior to Screening, or platelets in the 6 weeks prior to Screening, or the intention to donate blood within 3 months after the last Follow-up assessment.
11. Participation in another study within the last month (if single dose), or at least 4 months (if multiple dose), or within 10 times the half-life of the respective drug (whichever is longer) before Screening. For biologics, the minimum period is at least 6 months before Screening, the period of the pharmacodynamic effect, or 10 times the half-life of the respective drug, whichever is longer.
12. Subject is currently taking non-permitted concomitant medication. The subjects with normal hepatic function are restricted from use of any concomitant medications (including paracetamol) unless discussed and agreed with the Sponsor. In subjects with hepatic impairment, the use of prescribed medications is permitted for hepatic or concomitant disease as described in Section 6.3.1.
13. Not willing to abstain from consumption of coffee, tea, cola, energy drinks or chocolates from admission to the unit (Day -1) to discharge from the unit (Day 3).
14. Uncontrolled, or untreated hypertension defined as a mean of three repeated measurements of systolic blood pressure (SBP) >180 mmHg and/or diastolic blood pressure (DBP) >100 mmHg.
15. Subjects have estimated glomerular filtration rate (eGFR) <60 mL/min/1.73 m² as determined by Modification of Diet in Renal Disease (MDRD) formula.
16. Any condition associated with dehydration.
17. Female subjects:
 - a) who have a positive pregnancy test at Screening or on Day -1.
 - b) who are pregnant, lactating or planning to become pregnant during the study.

Hepatic impaired subjects (in addition)

18. Subjects with severe ascites or pleural effusion which will, in the opinion of the Investigator, adversely affect the subject's ability to participate in the study.
19. Subjects with severe encephalopathy (Grade III or IV).
20. Subjects with sclerosing cholangitis.
21. Serum albumin <2.0 g/dL.
22. Haemoglobin <10 g/dL.
23. Start of any new medication or any changes to a current dosage within 14 days before IMP administration.

Healthy subjects (in addition)

24. History or presence of any parenchymal hepatic disease.
25. Positive test for hepatitis B surface antigen (HBsAg) or hepatitis C virus antibody (HCVAb).
26. History of or active suicidal ideation, or suicide attempt as evidenced by positive response to either Question 4 (active suicidal ideation with some intent to act) or Question 5 (active suicidal ideation with specific plan and intent) on the C-SSRS (Screening Version; see Appendix 1 in Section 14).

